7.2 Multiple Ascending Dose (MAD) Cohort

7.2.1 Sample Size. The study sample size will be 24 for the MAD arm of the protocol in cohorts of 8. Participants will be randomized to treatment or placebo in a 3:1 ratio. The first 2 subjects of each cohort will be sentinels (1 treatment, 1 placebo). Continuation of the study in each cohort will occur if no clinical or biochemical adverse effects are observed in the sentinels as determined by the Safety Review Committee (SRC). Escalation to the higher dose will occur if no clinical or biochemical adverse effects are observed after a 10 day follow-up period as determined by the SRC.

7.2.2 LSALT Peptide Dosing. The doses for the MAD cohorts will be determined by the SRC based on the results from the prior SAD and MAD arms of the study. These doses have been determined to be 1 mg, 2.5 mg and 5 mg. LSALT peptide will administered intravenously once daily for 3 days. The starting dose for the Phase 1 clinical study will be subject to change and reassessed based on the results from the SAD cohort and in accordance with FDAs guidance document for estimating a safe starting dose in initial clinical trials.

7.2.3 Confinement. Participants will be confined for days -1 to day 4 during the administration of the LASLT peptide.

7.2.4 Replacement. In the event of participant drop-out, participants from the reserve pool will be enrolled in the study and randomized.

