3.3. Brief Description

This is a double-blind, placebo-controlled, randomized, adaptive design single and multiple ascending dose study to evaluate the safety and pharmacokinetics of LSALT peptide in healthy participants.

To establish a safe starting dose of LSALT peptide, unblinded low dose escalation will first be performed in a small cohort of participants. 0.01 mg of LSALT peptide will be administered intravenously (IV) once. If no adverse effects are observed following 72 hours, subsequent single (n=1) participants will be administered escalating doses of 0.1 mg, 0.3 mg and 0.5 mg every 72 hours. If no adverse effects are observed at the 0.5 mg dose, then the study will proceed to the first cohort of 8 participants (6 active treatment, 2 placebo per dose level) who will receive 1.0 mg of LSALT peptide in a double-blinded fashion. Safety, tolerability, PK and PD will be assessed before escalating to the next cohort. Dosing will be completed in two sequential cohorts of 8 participants using doses of 2.5 mg and 5.0 mg. The first 2 participants in each blinded cohort will act as sentinels (1 treatment, 1 placebo) who must show no adverse effects before continuing the study under the current design.

Once safety, PK and PD data are completed in the single ascending dose (SAD) cohort, and the LSALT peptide is determined to be safe and well-tolerated by the Safety Review Committee (SRC), the multiple ascending dose arm of the study will proceed. The multiple ascending dose arm will consist of 3 cohorts of 8 participants receiving 3 independent doses of the LSALT peptide or placebo once or twice daily for 3 consecutive days. The doses for this arm of the study will consist of the 3 highest doses determined by the SRC to be safe in the SAD cohort. The first cohort will receive drug in a double-blinded fashion. Safety, tolerability, PK, and PD will be assessed before escalating to the next cohort. Each cohort will consist of 6 active treatment, 2 placebo per dose level. The first 2 participants in each cohort will act as sentinels (1 treatment, 1 placebo) who must show no adverse effects before continuing the study under the current design.

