8.2. Derived PK Parameters

SAD:

The following plasma PK parameters will be derived for the SAD study portion.

Parameter	Definition	Method of Determination
AUC ₀₋₂₄	Area under the plasma concentration-time curve, from time 0 to 24 hours.	Linear trapezoidal method
AUC ₀₋₁₂	Area under the plasma concentration-time curve, from time 0 to 12 hours.	Linear trapezoidal method
AUC _{0-t}	Area under the plasma concentration-time curve, from time 0 to the last measurable concentration.	Linear trapezoidal method
AUC _{0-inf}	Area under the plasma concentration-time curve, from time 0 extrapolated to infinity.	AUC _{0-t} + C _{last} /λ _z , where C _{last} is the last measurable concentration.
%AUC _{exp}	Percentage of AUC _{0-inf} due to extrapolation from the time of last concentration to infinity.	(1 - AUC _{0-t} /AUC _{0-inf}) * 100

This document is confidential.

Parameter	Definition	Method of Determination
C_{max}	Maximum observed plasma concentration.	Observed directly from data
T_{max}	Time to reach C_{max} . If the maximum value occurs at more than 1 timepoint, T_{max} is defined as the first timepoint with this value.	Observed directly from data
$t_{1/2}$	Apparent first-order terminal elimination half-life.	$\ln(2)/\lambda_z$
λ_z	Apparent first-order terminal elimination rate constant.	Estimated by linear regression of the terminal elimination phase of the log-linear drug concentration-time curve
Cl/F	Apparent total body clearance.	Estimated as Dose/AUC _{0-inf}
V_z/F	Apparent volume of distribution.	Estimated as Dose/(\mathbf{\lambda}_z \times AUC_{0-inf})

MAD:

The following plasma PK parameters will be derived for the MAD study portion, for Day 1 and Day 3.

Parameter	Definition	Method of Determination
AUC_{0-24}	Area under the plasma concentration-time curve, from time 0 to 24 hours. (Day 1)	Linear trapezoidal method
AUC_{0-12}	Area under the plasma concentration-time curve, from time 0 to 12 hours. (Day 1)	Linear trapezoidal method
AUC_{0-tau}	Area under the curve over a dosing interval at steady state (Day 3 only)	Linear trapezoidal method
AUC_{0-t}	Area under the plasma concentration-time curve, from time 0 to the last measurable concentration.	Linear trapezoidal method
AUC_{0-inf}	Area under the plasma concentration-time curve, from time 0 extrapolated to infinity.	$AUC_{0-t} + C_{last}/\lambda_z$, where C_{last} is the last measurable concentration.

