$\%AUC_{exp}$	Percentage of AUC_{0-inf} due to extrapolation from the time of last concentration to	$(1 - AUC_{0-t}/AUC_{0-inf}) * 100$

This document is confidential.

Parameter	Definition	Method of Determination
	infinity.	
C_{max}	Maximum observed plasma concentration on.	Observed directly from data
T_{max}	Time to reach C_{max} . If the maximum value occurs at more than 1 timepoint, T_{max} is defined as the first timepoint with this value.	Observed directly from data
$t_{1/2}$	Apparent first-order terminal elimination half-life.	$\ln(2)/\lambda_z$
λ_z	Apparent first-order terminal elimination rate constant.	Estimated by linear regression of the terminal elimination phase of the log-linear drug concentration-time curve.
Cl/F	Apparent total body clearance.	Estimated as Dose/ AUC_{0-inf}
V_z/F	Apparent volume of distribution.	Estimated as Dose/ $(\lambda_z \times AUC_{0-inf})$
RAUC	Accumulation Ratio for AUC.	$AUC_{0-12} \text{ or } AUC_{0-24} \text{ Day 3} / AUC_{0-12} \text{ or } AUC_{0-24} \text{ Day 1}$
RC_{max}	Accumulation Ratio for C_{max} .	$C_{max} \text{ Day 3} / C_{max} \text{ Day 1}$

Note: λ_z will be the negative of the estimated slope of the linear regression of the log-transformed concentration (natural logarithm) versus time profile in the terminal elimination phase. At least three concentration points will be used in estimating λ_z . The time point where log-linear λ_z calculation begins (λ_z Lower), and the actual sampling time of the last quantifiable concentration used to estimate the λ_z (λ_z Upper) will be reported with the correlation coefficient from the linear regression to calculate λ_z .

Note: tau is the dosing interval for steady-state data.

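### Day 3 clearance and volume in the MAD part use a single-dose formula, which understates both if drug carries over from doses 1 and 2

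*SAP*

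**What the plan says.** SAP 8.2 introduces the MAD table with "The following plasma PK parameters will be derived for the MAD study portion, for Day 1 and Day 3". Some rows are then limited to one day: AUC0-24 and AUC0-12 are marked Day 1, and AUC0-tau is defined as "Area under the curve over a dosing interval at steady state (Day 3 only". The rows for "Apparent total body clearance" (Dose/AUC0-inf) and "Apparent volume of distribution" (Dose/(lambda_z x AUC0-inf)) have no day limit, so they apply on both days.

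AUC0-inf is the area "from time 0 extrapolated to infinity", computed as AUC0-t + Clast/lambda_z. Nothing is subtracted for drug already present before the dose. These are the same formulas as in the SAD table, where they are correct.

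The same MAD table plans an "Accumulation Ratio for AUC" and one for Cmax. On the dosing interval, protocol 7.2.2 says "LSALT peptide will administered intravenously once daily for 3 days", while SAP 3.3 still says "once or twice daily for 3 consecutive days".

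**The concern.** Dose/AUC0-inf estimates clearance when the area comes from that dose alone. After the third of three doses, the area from time 0 to infinity also includes the tails of doses 1 and 2. One dose is then divided by the area of more than one, so clearance comes out too low. Volume is too low by the same factor, because lambda_z does not change.

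The MAD parameter table reports both days. If there is carry-over, a reader comparing them would see clearance fall from Day 1 to Day 3 although nothing in the drug's disposition had changed. The plan sets out to measure accumulation, so its formulas should remain valid if accumulation is found.

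**Working it through.** The plan states no figure for this point, so there is none to reproduce.

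**Inputs**
- Three doses, once daily, tau = 24 h (protocol 7.2.2).
- Infusion over T = 2 h (protocol 10.1.6).
- Half-life: only the rat value is given, 0.66–1.17 h (protocol 3.5). The same section says work on volume of distribution, tissue distribution and excretion is still under way. Human half-life is therefore an assumption, shown up to 24 h.
- Linear one-compartment kinetics, with Day 3 time 0 at the start of the third infusion. Both are assumptions; the SAP does not define Day 3 time 0.

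**Formulas.** Let k = ln 2/half-life, r = exp(-k x tau) and g = (exp(kT) - 1)/(kT). The factor g allows for the 2-h infusion. By superposition, relative to the area of a single dose:
- Day 3 AUC0-inf = 1 + g(r + r²), so Dose/AUC0-inf gives true CL x 1/[1 + g(r + r²)].
- Day 3 AUC0-tau = 1 - g r³, so Dose/AUC0-tau gives true CL x 1/(1 - g r³).

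Example at 6 h: k = 0.1155, r = 0.0625, g = 1.125. Then g(r + r²) = 1.125 x 0.0664 = 0.0747, and 1/1.0747 = 0.930.

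| Half-life (assumed) | r | g | Dose/AUC0-inf ÷ true CL | Dose/AUC0-tau ÷ true CL |
|---|---|---|---|---|
| 4 h | 0.0156 | 1.195 | 0.981 | 1.000 |
| 6 h | 0.0625 | 1.125 | 0.930 | 1.000 |
| 8 h | 0.125 | 1.092 | 0.867 | 1.002 |
| 12 h | 0.25 | 1.060 | 0.751 | 1.017 |
| 24 h | 0.5 | 1.029 | 0.564 | 1.148 |

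At 1.17 h, the longer rat value, r is 6.7 x 10⁻⁷ and the error is below 0.001%. The error passes 5% at a half-life of roughly 5 to 6 h. Volume has the same ratios. Numerical integration of three 2-h infusions gives the same results. With tau = 12 h, the ratio at the third dose is already 0.856 for a 4 h half-life.

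**Effect of the sampling schedule.** The table assumes exact areas, but SAP 8.2 uses the linear trapezoidal rule. The protocol's MAD schedule (7.2.5) has no sample between 3 h and 24 h after the start of infusion. SAP 8.1 samples to 12 h after the end of infusion. Applying the trapezoidal rule to the model, with pre-dose and 24 h values available and quantifiable on Day 3:

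| Schedule, half-life | Dose/AUC0-inf ÷ true CL | Dose/AUC0-tau ÷ true CL |
|---|---|---|
| Protocol MAD, 4 h | 0.601 | 0.608 |
| Protocol MAD, 6 h | 0.704 | 0.743 |
| SAP 8.1, 6 h | 0.928 | 0.998 |

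On the protocol schedule, the straight line drawn across the gap overstates the area far more than carry-over does at these half-lives. On the SAP schedule, the formula change works as intended.

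**The case against.** The strongest objection is that this may never matter. The only half-life in the documents gives no measurable error with once-daily dosing, and the protocol's dense sampling just after the infusion suits a rapidly cleared drug. That stands. A reader might infer from the formula that Day 3 clearance in this trial will be understated by a tenth or a quarter. The documents do not support that, because those figures need human half-lives of about 8 to 12 h, which nothing in them suggests.

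Nor do the late samples show that accumulation is expected. The single-dose part also has a 72 h sample, and accumulation is impossible there. Planning accumulation ratios shows that the question is open, not which answer is expected.

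No Day 1 versus Day 3 test of clearance is planned. Clearance and volume are summarised descriptively (SAP 8.3), and the accumulation ratios do not use the disputed formula. A reader might also suspect the dose-proportionality slope, since SAP 8.4 includes Day 3 AUC0-inf. Under linear kinetics the factor 1 + g(r + r²) is the same at every dose, so it moves the intercept and leaves the slope unbiased.

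AUC0-tau is not a perfect denominator either. It is exact only at steady state, and at a 24 h half-life it overstates clearance by about 15%.

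These objections limit the weight of the point. They do not make the Day 3 formula correct: it gives a wrong value under the carry-over that the plan intends to measure.

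**Conclusion.** The Day 3 formulas for clearance and volume are mis-specified. Under linear kinetics they cannot overstate either parameter, and they understate both by the same fraction when drug carries over. The size depends on an unknown human half-life, from nil at the rat value to about -25% at 12 h, assuming one-compartment kinetics, once-daily 2-h infusions and exact areas.

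The consequence is confined to the reported Day 3 clearance and volume. Safety endpoints, accumulation ratios and the power-model slope are not affected. The /F label is unnecessary for an intravenous drug, but changing it alters no number. The point is worth correcting because the correction is cheap, not because a large error is likely.

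**What to change.** In the MAD table of SAP 8.2:
- For Day 3, define CL = Dose/AUC0-tau and Vz = Dose/(lambda_z x AUC0-tau), with tau equal to the dosing interval actually used. State that this is exact only at steady state (+0.2% at 8 h, +1.7% at 12 h, +15% at 24 h under the assumptions above).
- Alternatively, report CL and Vz from Day 1 only.
- Keep Dose/AUC0-inf for Day 1 and for the SAD part. The power-model list in SAP 8.4 need not change.

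Two related items need reconciling. The protocol and SAP differ on dosing frequency, which fixes tau. They also differ on the MAD sampling schedule: the gain depends on samples between 3 h and 24 h. AUC0-tau also needs a Day 3 value at time 0 and at the end of the interval. The protocol schedules a Day 3 pre-dose sample that SAP 8.1 omits. The protocol's 72 h sample, timed from the first infusion, falls 24 h after the third begins if doses are 24 h apart; SAP 8.1 should state the time origin of its own 72 h sample.

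The formula change costs two table cells and a footnote. It needs no new data if sampling follows SAP 8.1 and the protocol's pre-dose and 72 h samples are taken.

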8.3. Summary of PK Variables

Concentration:

Plasma concentrations will be listed and summarized, by nominal sampling time, and cohort/actual treatment. Concentrations below the quantification limit (BLQ) will be set to zero in summary tables. BLQ will be displayed in listings.

Individual subject and mean \pm SD profiles of the plasma concentration-time data will be plotted by dose level/cohort using actual and nominal times, respectively. These profiles will be presented on both linear-linear and log-linear scales.

This document is confidential.

For individual plots the BLQ values that occur in a profile before the first measurable concentration will be set to zero, and the BLQ values that occur after first measurable concentration will be set to missing. For mean plots, BLQ will be set to zero.

Parameters:

Plasma PK parameters will be listed and summarized descriptively by dose level/cohort.

For derivation of plasma pharmacokinetic parameters, the BLQ values that occur in a profile before the first measurable concentration will be set to zero. The BLQ values that occur after first measurable concentration will be set to missing.

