4.2. Pharmacokinetic Endpoints (Secondary)

The secondary PK endpoints are:

- Plasma LSALT concentrations.
- Plasma LSALT PK parameters.

This document is confidential.

5. Analysis Populations

All subjects' inclusion status into each analysis population will be determined after database lock and prior to unblinding for the final analysis.

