6.1. General Methods

SAS® for Windows, Release 9.4 (SAS® Institute Inc., Cary, NC, USA) software will be used to perform all data analyses.

All data in the database will be presented in the data listings. Unless otherwise stated, all listings will be sorted by cohort, randomized treatment group, subject number and assessment date/time. For the purposes of the summary tables, all subjects randomized to placebo will be combined into a single placebo group.

All listings and summaries/analyses will be presented separately for each study part. Unless otherwise stated, the descriptions of the analyses which follow, apply to both SAD/MAD study parts (Low Dose subjects' results will be listed only).

The following labels for treatment will be used on all tabulations where the results are displayed by treatment, in the following order:

SAD:

- All Placebo
- LSALT 1.0 mg
- LSALT 2.5 mg
- LSALT 5.0 mg

MAD:

- All Placebo
- LSALT 1.0 mg
- LSALT 2.5 mg
- LSALT 5.0 mg

Summary Statistics:

Unless otherwise stated, continuous variables will be summarized using the number of observations (n), and the statistics mean, median, standard deviation (SD), minimum and maximum. The minimum and maximum values will be presented to the same number of decimal places as recorded in the case report form (CRF), mean and median will be presented to one more decimal place than the raw data and the SD will be presented to two more decimal places than the raw data. Summaries of change-from-baseline variables will include only subjects who have both a baseline value and corresponding value at the timepoint of interest. Categorical variables will be summarized with frequency counts and percentages. Percentages will be rounded to one decimal place, with the denominator being the number of subjects in the relevant population, unless otherwise stated.

This document is confidential.

For the plasma PK data, the data will be rounded to two decimal places in the listings. Summary statistics will also include the geometric mean (three decimal places) and geometric coefficient of variation (CV) (%) (four decimal places). The geometric mean and CV(%) will not be calculated for T_{max} , $t_{1/2}$, $\%AUC_{exp}$ and λ_z .

Only data from nominal protocol scheduled visits will be included in the summary tables. Data from unscheduled visits will not be included in the summary tables (unless they were used as baseline) but will be included in the listings and figures.

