- Tabular display of data for medical history, prior/concomitant medications, and all tabular displays of adverse event data are presented by the body system, treatment class, or SOC with the highest occurrence in the active treatment group in decreasing order, assuming all terms are coded. Within the body system, drug class and SOC, medical history (by preferred term), drugs (by ATC1 code), and adverse events (by preferred term) are displayed in decreasing order. If incidence for more than 1 term is identical, they should then be sorted alphabetically. Missing descriptive statistics or p-values which cannot be estimated are reported as “-”.
- The percentage of subjects is normally calculated as a proportion of the number of subjects assessed in the relevant treatment group (or overall) for the analysis set presented. However, careful consideration is required in many instances due to the complicated nature of selecting the denominator, usually the appropriate number of subjects exposed. Describe details of this in footnotes or programming notes.
- For categorical summaries (number and percentage of subjects) where a subject can be included in more than one category, describe in a footnote or programming note if the subject are included in the summary statistics for all relevant categories or just 1 category and the criteria for selecting the criteria.
- Where a category with a subheading (such as system organ class) has to be split over more than one page, output the subheading followed by “(cont)” at the top of each subsequent page. The overall summary statistics for the subheading should only be output on the first relevant page.

14.2.5.3. *Listing Conventions*

- Listings will be sorted for presentation in order of treatment groups as above, subject number, visit/collection day, and visit/collection time.
- Missing data are represented on subject listings as either a hyphen (“-”) with a corresponding footnote (“- = unknown or not evaluated”), or as “N/A”, with the footnote “N/A = not applicable”, whichever is appropriate.
- Dates are printed in SAS DATE9.format (“ddMMMyyyy”: 01JUL2000). Missing portions of dates are represented on subject listings as dashes (--JUL2000). Dates that are missing because they are not applicable for the subject are output as “N/A”, unless otherwise specified.

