ATC2 Class Preferred Term	All Placebo (N=xxx)	etc. (N=xxx)
Subjects with at Least One Concomitant Medication	xx (xx.x%)	xx (xx.x%)
ATC2 A	xx (xx.x%)	xx (xx.x%)
Preferred Drug Name 1	xx (xx.x%)	xx (xx.x%)
Preferred Drug Name 2	xx (xx.x%)	xx (xx.x%)
ATC2 B	xx (xx.x%)	xx (xx.x%)
Preferred Drug Name 1	xx (xx.x%)	xx (xx.x%)
Preferred Drug Name 2	xx (xx.x%)	xx (xx.x%)
etc.		

Concomitant medications coded using WHO Drug Version X.X.

Concomitant medications are medications taken at least once on or after first study drug administration. Medications stopping on the same day as study drug administration are considered as concomitant medications.

ATC = Anatomic Therapeutic Chemical, WHO DD = World Health Organization Drug Dictionary (WHO DD) Version.

Table 14.1.4.3 Exposure - MAD (Safety Population)

Administered Dose	All Placebo (N=xxx)	etc. (N=xxx)
Day 1 Dose	xx (xx.x%)	xx (xx.x%)
Day 2 Dose	xx (xx.x%)	xx (xx.x%)
Day 3 Dose	xx (xx.x%)	xx (xx.x%)

Programming Note: Also include a Total column.

Table 14.2.1.1.1.2 Plasma Pharmacokinetic Concentrations - SAD (Pharmacokinetic Concentration Population)

Concentration (unit)	Visit Scheduled Timepoint	LSALT 1.0 mg (N=xxx)	etc. (N=xxx)
Concentration (unit)			
Day 1			
XX Hours Pre-dose			
n		xx	xx
Mean (SD)		xx.xx (xx.xxxx)	xx.xx (xx.xxxx)
Median		xx.xx	xx.xx
Min, Max		xx.x, xx.x	xx.x, xx.x
Geometric Mean		xx.xx	xx.xx
CV% Geometric Mean		xx.xxxx	xx.xxxx
etc.			

Programming Note: Continue for all protocol scheduled visits/timepoints.

Table 14.2.1.1.1.3 Plasma Pharmacokinetic Concentrations - MAD (Pharmacokinetic Concentration Population)

Concentration (unit)	LSALT XX mg (N=xxx)	etc. (N=xxx)
Visit		
Scheduled Timepoint		
Concentration (unit)		
Day 1		
XX Hours Pre-dose		
n	xx	xx
Mean (SD)	xx.xx (xx.xxx)	xx.xx (xx.xxx)
Median	xx.xx	xx.xx
Min, Max	xx.x, xx.x	xx.x, xx.x
Geometric Mean	xx.xx	xx.xx
CV% Geometric Mean	xx.xxxx	xx.xxxx
etc.		

Programming Note: Continue for all protocol scheduled visits/timepoints.

Figure 14.2.1.1.2.2 Individual Plasma Pharmacokinetic Concentrations by Treatment Group - SAD (Pharmacokinetic Concentration Population)

Plots of individual plasma concentrations over time, by treatment group for each subject

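### Does setting BLQ concentrations to zero, while asking for geometric means and CVs, leave the concentration tables undefined or biased?

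*SAP*

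**What the plan says.** For plasma concentrations, SAP 8.3 (Summary of PK Variables) states: "Concentrations below the quantification limit (BLQ) will be set to zero in summary tables". For plasma PK data in general, SAP 6.1 (General Methods) adds: "Summary statistics will also include the geometric mean (three decimal places) and geometric coefficient of variation (CV) (%) (four decimal places". The exemption in 6.1 ("The geometric mean and CV(%) will not be calculated for") covers only Tmax, half-life, the extrapolated share of AUC and the terminal rate constant, so concentrations are not exempt. The shells for Tables 14.2.1.1.1.2 (SAD) and 14.2.1.1.1.3 (MAD) carry both geometric rows, use a pre-dose time as their example, and end with "Programming Note: Continue for all protocol scheduled visits/timepoints".

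Two other rules bear on the point. SAP 14.2.5.2 (Table Conventions) gives a display rule: "Missing descriptive statistics or p-values which cannot be estimated are reported as" a dash. SAP 8.3 has a separate rule for parameters: "For derivation of plasma pharmacokinetic parameters, the BLQ values that occur in a profile before the first measurable concentration will be set to zero", with BLQ values after the first measurable one treated as missing.

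**The concern.** A geometric mean needs the logarithm of every value, and zero has none. Three instructions therefore seem to collide: enter zeros, compute log-based statistics, and do so at all times, including pre-dose, where every value should be BLQ.

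The dash in 14.2.5.2 plainly covers a row in which every value is BLQ. It does not say whether a single zero among six makes the statistic non-estimable. A program whose log step returns a missing value for zero would compute the geometric mean from the quantifiable subjects alone, while n, mean, SD, median, minimum and maximum in the same column use everyone. Every dropped value lies below every retained one, so the geometric mean would be too high and the geometric CV would usually be too low.

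"Plasma LSALT concentrations" is a named secondary endpoint in SAP 4.2, so two programmers producing different rows from one plan would be a fair criticism.

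**Working it through.** **1. What a zero does.** The geometric mean is GM = exp(mean of ln x). The geometric CV is GCV = 100 × √(exp(s²) − 1), where s is the SD of ln x. With one zero in the row, the GCV is undefined and the GM is either 0 (as a root of a product) or undefined.

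**2. The four BLQ rules in SAP 8.3, side by side.**

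| Use | BLQ before first measurable value | BLQ after it |
|---|---|---|
| Summary tables | zero | zero |
| Mean plots | zero | zero |
| Individual plots | zero | missing |
| Parameter derivation | zero | missing |

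The authors say missing where they want a value left out. For summary tables they say zero, and for mean plots likewise: "For mean plots, BLQ will be set to zero". Dropping zeros at the log step would treat them as missing, which is not the rule written for tables.

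**3. Applying 8.3 together with 14.2.5.2.**
- No BLQ value in the row: geometric statistics as usual.
- All values BLQ (expected at Day 1 pre-dose): a dash.
- Mixed row: the zeros are data, the GCV cannot be estimated, and it is shown as a dash. The GM is 0 or a dash. That remaining choice is cosmetic.

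**4. Size if a program dropped zeros anyway.** The quantification limit, BLQ share and between-subject CV are not in the documents. I assume log-normal data, a BLQ share q and a true CV of 30% or 50%.

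σ = √ln(1 + CV²), which gives 0.294 at 30% and 0.472 at 50%. With a = Φ⁻¹(q) and λ = φ(a)/(1 − q), the GM is inflated by the factor exp(σλ), and the retained log-variance is σ²(1 + aλ − λ²).

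For q = 1/3: a = −0.431 and λ = 0.545, so exp(0.294 × 0.545) = 1.17 and exp(0.472 × 0.545) = 1.29.

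| BLQ share | GM factor, CV 30% | GCV, CV 30% | GM factor, CV 50% | GCV, CV 50% |
|---|---|---|---|---|
| 1/6 | 1.09 | 23.4% | 1.15 | 38.5% |
| 1/3 | 1.17 | 20.3% | 1.29 | 33.2% |
| 1/2 | 1.26 | 17.8% | 1.46 | 29.1% |

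Simulation of 200,000 cohorts of 6, with 1 to 4 values dropped, gives a higher GM in every cohort and a lower GCV in 91–93% of them. The GCV can also rise. With a limit of 1, the values 0.95 (BLQ), 1.05, 1.1, 1.15, 1.2 and 6.0 give 79.8% with all six and 87.0% after dropping the first.

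**5. How many rows could be mixed.** At a time with a 20% BLQ probability, the chance of at least one BLQ value among 6 is 1 − 0.8⁶ = 74%. The only half-life in the documents is 0.66–1.17 h (Protocol 3.5), from rats at 100–450 mg/kg. If it carried over to humans, the BLQ probability would climb from 5% to 95% over 2 × 1.645 × σ × half-life / ln 2:
- 0.66 h, CV 30%: 0.92 h
- 1.17 h, CV 50%: 2.62 h

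On the SAP's SAD schedule that covers 0–2 sampling times if the crossing falls after 2 h, and up to 4–5 if it falls earlier, where samples are closer together. This shows only that mixed rows are plausible.

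**6. What the reader would see.** Take 1.2, 1.5, 2.0 and three BLQ values. With zeros kept, the mean is 4.7/6 = 0.78, the median is (0 + 1.2)/2 = 0.60 and the minimum is 0. With zeros dropped, the GM is (1.2 × 1.5 × 2.0)^(1/3) = 1.53 and the GCV is 26%. A positive GM beside a minimum of 0 is impossible on the same six values, so the slip would show in the table itself.

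**The case for a change.** The strongest opposing case is that 14.2.5.2 is a display rule. It gives the symbol for a statistic that cannot be estimated, but not the condition under which a geometric mean counts as such. Section 8.3 takes the trouble to give BLQ rules for tables, two kinds of plot and parameters, and leaves only the log-based table rows without one. Interim descriptive statistics come from WinNonlin (SAP 11) and final tables from SAS (SAP 14), so two programs with different defaults may handle the same zeros. BLQ values are also foreseeable: SAD sampling runs to 72 h, and Protocol 3.5 puts 90% or more of the peptide in human whole blood inside cells, while the tables report plasma.

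It stands that no sentence names the mixed row, and that such rows may occur. The claim of bias does not stand as a property of the plan. It describes what a program might do against the written rule, and the shell prints the minimum in the same column while the listings show BLQ entries. A GM above the arithmetic mean would be a second warning, though a less dependable one. It occurs in 99–100% of mixed rows at a CV of 30–50% and a BLQ share of 20–50%, but in only 71–90% at a CV of 80% and a BLQ share of 5–20%.

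**Conclusion.** No change to the plan follows. This is a missing detail that an analyst fills from the text: zero means zero in the tables, a log-based statistic with a zero in it cannot be estimated, and the dash is already provided. A sentence saying so would restate what 8.3 and 14.2.5.2 imply. A count of BLQ values per row would be a reporting preference.

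If zeros were dropped in error, the geometric mean would be too high by about 9–46%, and the geometric CV usually though not always too low, for true CVs of 30–50% and BLQ shares of one sixth to one half. All of this rests on assumed log-normality, CV and BLQ share. The error would stay within two descriptive tables. AUC, Cmax and the power model in SAP 8.4 use the separate parameter rule, and the mean and SD promised in Protocol 16.0 can be computed at every time. No conclusion is shown to depend on the geometric rows.
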